## BACKGROUND

Globally, 136 million births are reported annually (Sintayehu et al., 2020) and about, 4 million birth suffer respiratory distress (Garvey & Dempsey, 2020). where 10% entail simple resuscitative efforts while 0.1% need advanced measures to initiate breathing (Yeo et al., 2020). Despite all the efforts three-quarters of neonatal deaths occur due to asphyxia (Liu et al., 2016). Unfortunately, 98% of these deaths occur in low, and middle-income countries (Garces et al., 2017; Mildenberger, Ellis, & Lee, 2017) in which Pakistan is ranked on 3rd among countries that have the highest neonatal deaths (Afshan, Narjis, & Qayyum, 2019). The neonatal mortality rate in Pakistan is reported as 46/1000 live births (UNICEF, 2018). It is suggested that 30% of these deaths can be prevented through provision of trained emergency birth attendants (Ashish et al., 2017; Shikuku, Milimo, Ayebare, Gisore, & Nalwadda, 2018) in which education plays an integral role.

Nurses are the largest workforce in the healthcare system that are directly engaged in the provision of newborn care. Therefore, they should be conversant and competent in emergency newborn management. However, the majority of them are not skillful in the respective field (Budhathoki, Gurung, Ewald, Thapa, & KC, 2019). The situation is not very different when we are talking about nursing students, our future work force often reported unprepared and lacking the confidence in basic lifesaving skills such as resuscitation (Carolan-Olah et al., 2018; Malarvizhi, Glory, Rajeswari, & Vasanthi, 2017; Tastan et al., 2017).

Though, Pediatric care is a basic component of the nursing curriculum, instituting resuscitation as a vital part of students competencies during their undergraduate studies (Tastan et al., 2017). Yet, studies reported nursing students possess inadequate knowledge in the respective field (Malarvizhi et al., 2017). The skills of nursing students might be affected positively and

negatively due to their training during their undergraduate studies. Since, it is well documented that effective educational programs in preservice settings such as schools of midwifery, nursing, and medicine, established more active forms of lifelong learning to improve the quality of care (Singhal, McMillan, Savich, Matovelo, & Kamath-Rayne, 2020). However, like many other developing countries in Pakistan, the education of nursing students is mostly based on traditional methods that are lacking the component of adequate learning and training in neonatal resuscitation (Huang et al., 2019; Pinar, Akalin, & Abay, 2016), resulting an insufficient knowledge among many trainees on assessment (Huang et al., 2019). Recently, several studies compare traditional methods of educational intervention with integrating new strategies and conclude that new methods are indispensable for nursing education (Kim & Ahn, 2019a; Pinar et al., 2016).

The “Learn, See, Practice, Prove, Do, and Maintain” (LSPPDM) pedagogy is one of such frameworks synthesized after intensely reviewing the literature and acting as a guiding path in teaching and learning of procedural skills (Sawyer et al., 2015). It is augmented that it can impart its role in the improvement of clinical practice resultant to increase patient satisfaction in hospitals (Sawyer et al., 2015). The major goal of LSPPDM pedagogy is to learn a psychomotor skill, accomplishing aptitude, and upholding skill once attained. It is based on adult learning theory that can support the acquisition and maintenance of skills in the area of neonatal resuscitation (Ades & Lee, 2016).

As Knowledge is considering a prerequisite for competence in skill performance and to evaluate the effectiveness of an educational program self -efficacy measurement is an important tool (Mendhi, Premji, Cartmell, Newman, & Pope, 2020). Moreover, a positive relationship is reported between nursing students' knowledge and self-efficacy, both in turn enhancing skill in the

concerned area (Kim & Ahn, 2019b). Thus, the important variables knowledge, self-efficacy, and skill have been selected for this study.

To the best of researcher knowledge, no published literature was found on this topic in the context of Pakistan. While little published literature is available at the international level. Hence, this was the first study to determine the efficacy of the LSPPDM framework in the teaching and learning of neonatal resuscitation among undergraduate nursing student's knowledge, skill, and self-efficacy conducting at the College of Nursing, Allama Iqbal Medical College, Lahore, Pakistan. The study may provide a groundwork for future trials to investigate the retaining effect that is potentiating through an instructor directing with additional self-directing learning during education.

## **OBJECTIVES**

The study objective was to:

1. Compare the difference in knowledge among undergraduate nursing students learning of neonatal resuscitation through “Learn, See, Practice, Prove, Do, Maintain pedagogy” as compared to those who had learned through the traditional method.
2. Compare the difference in skill among undergraduate nursing students learning of neonatal resuscitation through “Learn, See, Practice, Prove, Do, Maintain pedagogy” as compared to those who had learned through the traditional method.
3. Compare the difference in self-efficacy among undergraduate nursing students learning of neonatal resuscitation through “Learn, See, Practice, Prove, Do, Maintain pedagogy” as compared to those who had learned through the traditional method.

## **HYPOTHESIS**

So, the hypothesis was generated as follows:

- a) Hypothesis  $H_0$  a: There is no difference in knowledge among undergraduate nursing students learning of neonatal resuscitation through LSPPDM Pedagogy as compared to those who had learned through the traditional method.
- b) Hypothesis  $H_0$  b: There is no difference in skill among undergraduate nursing students learning of neonatal resuscitation through LSPPDM Pedagogy as compared to those who had learned through the traditional method.
- c) Hypothesis  $H_0$  c: There is no difference in self-efficacy among undergraduate nursing students learning of neonatal resuscitation through LSPPDM Pedagogy as compared to those who had learned through the traditional method.

The alternative hypothesis was as follow:

- a) Hypothesis  $H_1$  a: There is a difference in knowledge among undergraduate nursing students learning of neonatal resuscitation through LSPPDM Pedagogy as compared to those who had learned through the traditional method.
- b) Hypothesis  $H_1$  b: There is a difference in skill among undergraduate nursing students learning of neonatal resuscitation through LSPPDM Pedagogy as compared to those who had learned through the traditional method.
- c) Hypothesis  $H_1$  c: There is a difference in self-efficacy among undergraduate nursing students learning of neonatal resuscitation through LSPPDM Pedagogy as compared to those who had learned through the traditional method.

## METHODS

### Study design and Setting

A Single-blind Randomized Control Trial adheres to the CONSORT guiding principle (Figure 1).

The setting was the college of Nursing, Allama Iqbal Medical College, Lahore Pakistan, a specialized tertiary level educational center in the public sector that offers (2 & 4year) graduation in nursing and 1-year post basic specialization in various disciplines. The participants were 3rd and 4th professional B.sc nursing students (4 years) enrolled in the current year of 2020-2021.

**Duration of Study:** October 2020 to March 2021.

**Sample Size:** The sample size is calculated using the *OpenEpi* software (Kim & Ahn, 2019b) The calculated sample size is 24 (12 in each group). This sample size is small to perform the statistical test with good efficacy. So, 30 in each group will be taken,  $n = 60$  (30 in each group). After adding a 20% dropout rate the final sample size will become 72 (36 in each group).

The sample size is calculated using the following information and formula;

$$n = \frac{(Z_{1-\beta} + Z_{1-\alpha/2})^2 + (\delta_1^2 + \delta_2^2)}{(\mu_1 - \mu_2)^2}$$

$\alpha$	5%
$1 - \alpha$	95%
$1 - \beta$	80%
$Z_{1-\alpha/2}$	1.96
$Z_{1-\beta/2}$	2.58
$\mu_1$ Expected mean in Skill in intervention Group (LSPPDM Pedagogy)	8.71(Kim & Ahn, 2019b).

$\mu_2$ Expected mean in Skill in Control (Traditional)	7.03(Kim & Ahn, 2019b).
$\delta_1$ Expected standard deviation in Skill Intervention (LSPPDM Pedagogy)	1.48(Kim & Ahn, 2019b).
$\delta_2$ Expected standard deviation in Skill in Control (Traditional)	1.33(Kim & Ahn, 2019b).
n Expected sample size in each group	24

Sample Size For Comparing Two Means			
Input Data			
Confidence Interval (2-sided)	95%		
Power	80%		
Ratio of sample size (Group 2/Group 1)	1		
Group 1		Group 2 Difference*	
Mean	8.71	7.03	1.68
Standard deviation	1.48	1.33	
Variance	2.1904	1.7689	
Sample size of Group 1	12		
Sample size of Group 2	12		
Total sample size	24		

**Sampling Technique:** Simple random sampling.

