## **DATA COLLECTION PROCEDURE**

### **Recruitment:**

The list of all nursing students in the 3rd and 4th professional was developed and the participants were recruited through simple random sampling. Initially, 62 participants (31 in each group) meet the inclusion criteria. Two participants were dropped in the follow-up for personal reasons one was not attending the full course of intervention and the other was absent on the days of evaluation. Thus, yielding a total of 60 participants (30 in each group).

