## **DATA ANALYSIS PLAN**

The data were analyzed by using Statistical Package for the Social Sciences (SPSS) version 25. Mean and SD were given for age, knowledge score, skill score and self-efficacy score. Frequency and percentage were given for education, language, marital status, division in previous result, residential area and previous neonatal resuscitation exposure. Both groups tested for homogeneity in general and resuscitation specific characteristics using  $\chi^2$  -test, and t-test. Independent sample t test was used to compare the mean age, knowledge score, skill score and self-efficacy score between both groups. Paired t test was used to compare the pre and post education knowledge, skill and self-efficacy score in both groups. Chi square / Fisher's exact test was used to compare the education level, language, marital status, division in previous result, residential area and previous neonatal resuscitation exposure between both groups. A p-value  $\leq$  0.05 was taken as significant.

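### The software sample size (12 per group, 24 in total) reproduces, but the parameter table beside it misstates the power z and the per-group n, and 72 does not keep 60 after a 20% dropout rate

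*Combined protocol and SAP*

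**What the plan says.** All the planning figures stand in the Sample Size paragraph and tables under METHODS, Study design and Setting.

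- **Text:** "The calculated sample size is 24 (12 in each group"). This is judged too small, and the target is raised: "So, 30 in each group will be taken", a total of 60. Then: "After adding a 20% dropout rate the final sample size will become 72 (36 in each group").
- **Parameter table:** alpha 5%, power 80%, a z of 1.96 for alpha, and a z of 2.58 in a row labelled Z(1-beta/2). The expected skill means are 8.71 and 7.03, with SDs 1.48 and 1.33. The last row, "n Expected sample size in each group", is filled with 24.
- **OpenEpi output:** "Confidence Interval (2-sided) 95"%, power 80%, ratio 1, and the same means and SDs. The row "Sample size of Group 1" shows 12, Group 2 also shows 12, and the total is 24.

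The DATA ANALYSIS PLAN names the test: "Independent sample t test was used to compare the mean age, knowledge score, skill score and self-efficacy score between both groups". The Recruitment section reports 62 participants (31 per group), two of whom were lost: "Thus, yielding a total of 60 participants (30 in each group").

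**The concern.** A reader should be able to rebuild the sample size from the printed inputs. Here the parameter table disagrees with the power stated a few rows above it and with the software output printed below it. Someone working from the table would not reach 12 per group, and could take 24 per group to be the calculated requirement, twice the true figure.

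The dropout step raises a separate question. A dropout rate is normally a share of those enrolled. If 20% of the enrolled students are lost, the number enrolled has to be the target divided by 0.80. Multiplying the target by 1.20 gives a smaller number. If the allowance is too small, the trial could end below its own target of 30 per group.

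**Working it through.** **Inputs** (all from the Sample Size tables): means 8.71 and 7.03; SDs 1.48 and 1.33; two-sided alpha 5%; power 80%; equal arms.

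- Difference: 8.71 - 7.03 = 1.68; squared, 2.8224.
- Variance sum: 2.1904 + 1.7689 = 3.9593.

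**Reproducing the plan's own figure.** The usual formula for two means is

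n per group = (z for alpha + z for power)^2 x (variance sum) / (difference)^2

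= (1.96 + 0.842)^2 x 3.9593 / 2.8224 = 11.01, rounded up to 12 per group and 24 in total.

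This matches the text and the OpenEpi output. With the planned t-test, 12 per group gives 79.8% power (noncentral t), in effect the stated 80%.

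**Power z.**

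| Reading | z |
|---|---|
| Z(1-beta), power 80% | 0.842 |
| Z(1-beta/2), as the row is labelled, beta 20% | Z(0.90) = 1.282 |
| Printed | 2.58, which is Z(0.995) |

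The printed value fits neither reading. Put into the formula above, it gives (1.96 + 2.58)^2 x 3.9593 / 2.8224 = 28.9, so 29 per group. That is neither 12 nor 24, so 2.58 did not produce the stated result.

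**Row for n.** The table puts 24 in each group. The text and the OpenEpi output both put 12 in each group and 24 in total. The calculation agrees with 12.

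**Dropout.**

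- How 72 arises: 60 x 1.20 = 72.
- A 20% loss from 72 leaves 72 x 0.80 = 57.6, or 36 x 0.80 = 28.8 per group. The target is 60 (30 per group).
- Loss that 72 does cover: (72 - 60) / 72 = 12/72 = 16.7%.
- Number needed to keep 60 after a 20% loss: 60 / 0.80 = 75. By arm, 30 / 0.80 = 37.5, so 38 per group and 76 in total.

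**Effect on power.** The averaged SD is sqrt(3.9593/2) = 1.407, so the standardised difference is 1.68/1.407 = 1.194. Two-sided 5% t-test power, equal arms:

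| Per group | Power |
|---|---|
| 12 | 79.8% |
| 28 | 99.2% |
| 29 | 99.4% |
| 30 | 99.5% |

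**Printed formula.** In the text available for this review, the formula has a plus sign between the squared z sum and the variance sum. Read that way, even with z = 0.842, it gives (7.85 + 3.96) / 2.8224 = 4.2, not 12. The plus sign may come from the conversion of the PDF, so it is something to check and not a finding.

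**The case against.** The dropout sentence has a fair defence. It speaks of adding 20%, and adding 20% to 60 does give 72. Nor is 60 a computed requirement: the calculation gives 24, and the plan raises it by judgement. A 20% loss from 72 would still leave more than twice the calculated size. This makes the dropout item the mildest of the three, but it does not remove it. The sentence calls the 20% a dropout rate and the previous one sets 30 per group, and 36 per group does not keep 30 at that rate.

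It can also be said that nothing practical follows. The Recruitment section reports 2 losses among 62 participants (3.2%) and 60 completers, so the allowance was never tested. That stands, and it limits the point to reporting. (That 62 took part where 72 were planned is a separate matter.)

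No comparable defence exists for the two table rows. No reading of the z label gives 2.58, and 24 per group cannot be squared with 12 per group in the same section.

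A reader might infer that the calculated size is itself wrong, or that the trial was underpowered for skill. The documents support neither inference: 12 per group reproduces, and 30 per group completed.

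**Conclusion.** Three figures are wrong as written, and the point is minor.

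- The z for power is printed as 2.58; for the stated 80% power it is 0.842.
- The per-group n is printed as 24; it is 12, and 24 is the total.
- The final size of 72 covers a 16.7% loss among those enrolled, not 20%. It is 3 short of 75, or 4 short of 76 with equal arms.

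The error in the dropout step lies in what 72 is said to allow for. The addition itself is correct: 60 plus 12 is 72.

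The power figures of about 99% at 28 to 30 per group rest on the plan's own means and SDs for skill, equal arms and independent observations. They say nothing about knowledge or self-efficacy, for which the plan gives no planning values.

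**What to change.** 1. Replace the row Z(1-beta/2) = 2.58 with Z(1-beta) = 0.842.
2. Change the per-group n row from 24 to 12, or keep 24 and relabel the row as the total.
3. Restate the dropout sentence so that it says what 72 does, for example: *The target of 60 was increased by 20% to 72 (36 per group), which keeps 60 if up to 16.7% of those enrolled are lost.* For reference, keeping 60 after a true 20% loss would need 75, or 76 with equal arms.
4. Check in the source file that the formula multiplies the squared z sum by the variance sum. If the plus sign is really there, correct it as well; otherwise the corrected rows still would not lead to 12.

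The cost is one reworded sentence, two table rows and one check of the formula. No enrolment, power statement or analysis changes.

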**Sample Selection:**

**Inclusion Criteria:**

The nursing students were included in the study who:

- Were currently enrolled in the Bachelor of Science in Nursing (4 years) 3rd and 4th Professional.
- Those willing to attend the full course of neonatal resuscitation.
- Had age 18-28 years.
- Those willing to give informed consent.

**Exclusion Criteria:**

The nursing students were excluded who:

- Were on leave from that period
- Had already received any educational training on neonatal resuscitation.
- Working as Nursing Assistants in Clinical Setting.

[figure not shown]

Figure 1. Consort Diagram

## **EQUIPMENTS:**

- Multimedia
- Low fidelity Neonatal Simulator
- Mannequins
- Hand out for theoretical content

## **EDUCATIONAL INTERVENTION**

A 6-week educational intervention was given to both groups.

### **1) Traditional method of neonatal resuscitation (Traditional Group)**

Traditional group was learned through the 2-step traditional method constituted of 2 didactic lectures/ week leading towards the second step of 1 skill session/week for 1 hour. The lecture content was the same for both groups and was prepared from the Textbook of Neonatal Resuscitation 7th edition of the American Association of Pediatrics (Nimbalkar et al., 2015). The lecture's content is based on foundations, Preparation, initial steps, positive pressure ventilation, endotracheal intubation, chest compression, medication, post-resuscitation care, and ethics in resuscitation. The students practice their skills under instructor supervision on the mannequins in groups of ratios 4-5 in each group errors were corrected immediately.

### **2) LSPPDM pedagogy method of neonatal resuscitation learning (Pedagogy Group)**

The pedagogy group was taught through the 6-steps LSPPDM pedagogy instituted in 2 lectures/week + video+ 2skill sessions/week for 1 hour. In the 1st step (learn) didactic lectures were given to the students leading to the second step (see), a video on neonatal resuscitation (<https://youtu.be/8yqP5m1jiPE>) was added. In the 3rds step (practice) students practice their skill on a low fidelity simulator under instructor supervision in a ratio of 4-5 in each group. The errors were corrected on the spot. In the 4th step (prove) students proving their skill through the checklist

to enhance their learning and memory. In the 5th step (do) students observed neonatal resuscitation in real-life situations through the clinical rotation. Finally, the 6th step (maintain) was established through additional skill sessions/week for one hour in groups under self-directed learning.

## **DATA COLLECTION PROCEDURE**

### **Recruitment:**

The list of all nursing students in the 3rd and 4th professional was developed and the participants were recruited through simple random sampling. Initially, 62 participants (31 in each group) meet the inclusion criteria. Two participants were dropped in the follow-up for personal reasons one was not attending the full course of intervention and the other was absent on the days of evaluation. Thus, yielding a total of 60 participants (30 in each group).

### **Randomization and Allocation:**

The students allocated from each professional in traditional group and Pedagogy group through the Lottery method (Moon & Hyun, 2019). The difference in the professional year was overcome through equal distribution of each professional student in both groups. Allocation of participants was concealed using envelop method.

### **Blinding:**

Masking of data assessment was provided by assigning a code to each student. The facilitators, who assessed the student's skills, endure uninformed regarding the student's allocation status and sequence of the scenario in the pre-and post-data collection.

### **Study Variables:**

#### **Independent Variable:**

1. The Educational intervention is the independent variable was measured either through LSPPDM pedagogy, a six-step method, and a traditional 2 step method.

**Dependent Variable:** The dependent variable were:

1. Knowledge was measured through 17-item multiple-choice questions adopted from Knowledge Questionnaire (Milededer, Gressl, Urlesberger, & Raith, 2019).
2. Self-efficacy measured through a 23-item scale called the Self-Efficacy for Neonatal Resuscitation Instrument (Nyiringango, 2019).
3. Skill was measured through a 30 item checklist for measuring technical skills and the non-technical skills were measured through a 9-item checklist on a 5-point Likert scale in neonatal resuscitation (Rovamo, Mattila, Andersson, & Rosenberg, 2011).

### **Methods for Collection of Data:**

Two facilitator evaluators were trained regarding the scoring of each scale in a two-hour workshop before data collection (Kirkpatrick, Cantrell, & Smeltzer, 2019). The data was collected at two points in time in the Simulation lab.

- 1st-time data was collected as a pre-test before the educational intervention.
- The 2nd-time data was collected after 6 weeks of educational intervention.

### **Evaluation Environment:**

On the day of evaluation, students were divided into pairs. Each pair was performed on two scenarios in which one was acting as a leader and the other was the helper and were change their positions in the second scenario (Rubio-Gurung et al., 2014). The procedure was classified into assessment, preparation, initial newborn care, positive pressure ventilation, intubation, chest compressions medications, and reporting. All the simulation scenarios were performed in a simulated delivery room situation. Where two student facilitators were present. One was acting

like a pregnant lady while the other was performing the role of a delivery nurse and present the simulation scenario in a standardized fashion to each participant.

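### Skill is assessed in leader/helper pairs and allocation is balanced by professional year, but the planned t-test ignores both; how pairs relate to arm is not stated, so the direction of the error is unknown

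*Combined protocol and SAP*

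**What the plan says.** All references are to the combined protocol and SAP.

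- **Evaluation Environment:** "On the day of evaluation, students were divided into pairs". Each pair worked through two scenarios, in which "one was acting as a leader and the other was the helper and were change their positions in the second scenario". The section does not say whether partners shared an arm, or whether the checklist score belonged to the leader, to each student or to the pair.
- **Randomization and Allocation:** "The difference in the professional year was overcome through equal distribution of each professional student in both groups".
- **Data Analysis Plan:** "Independent sample t test was used to compare the mean age, knowledge score, skill score and self-efficacy score between both groups". No term for pair or professional year appears, and no other section deals with either.
- **Recruitment:** 62 students at the start, 31 per arm. "Thus, yielding a total of 60 participants (30 in each group").
- **Educational Intervention:** students practised "in groups of ratios 4-5 in each group errors were corrected immediately" (traditional arm) or "under instructor supervision in a ratio of 4-5 in each group" (pedagogy arm). Nothing says that membership of these groups was fixed.
- **Blinding:** "Masking of data assessment was provided by assigning a code to each student". The section is silent on how pairs were made up.

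**The concern.** A student's checklist score depends partly on the partner's actions, and the student who leads second has just helped in the first scenario. Partners' scores are therefore likely to be correlated. An independent-sample t-test takes the 30 scores in each arm as independent.

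The consequence depends on how pairs were formed. With positive correlation, same-arm pairs make the t-test's standard error too small and cross-arm pairs make it too large. If pairing ignored arm, the two effects roughly cancel. Separately, balancing the arms by year and then leaving year out of the analysis makes the standard error too large whenever year predicts the score.

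Skill is one of the three hypotheses and the outcome used to size the trial. As the plan stands, a reader cannot tell whether its p-value is too small, too large or about right.

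**Working it through.** **Inputs.** Means 8.71 and 7.03 (difference 1.68), SDs 1.48 and 1.33, two-sided 5%, power 80% (Sample Size); 30 per arm analysed (Recruitment). The within-pair correlation ρ is not in the documents; 0.1 to 0.5 is assumed.

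**The plan's own figure.** n per arm = (1.96 + 0.84)² × (1.48² + 1.33²) / 1.68² = 11.01, rounded up to 12. This reproduces the stated 12 per group, which assumes independent students.

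**Size of the nominal 5% t-test.** Pairing multiplies the variance of the arm difference by a design effect (DE): 1 + ρ if all pairs are same-arm, 1 − ρ if all are cross-arm. True size ≈ 2 × [1 − Φ(1.96/√DE)].

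| ρ (assumed) | Same-arm: DE, size | Cross-arm: DE, size |
|---|---|---|
| 0.1 | 1.1, 0.062 | 0.9, 0.039 |
| 0.3 | 1.3, 0.086 | 0.7, 0.019 |
| 0.5 | 1.5, 0.110 | 0.5, 0.006 |

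Simulating the t-test at 30 per arm (100,000 runs) gives 0.061, 0.087, 0.112 for same-arm pairs and 0.040, 0.020, 0.007 for cross-arm pairs. Pairing at random without regard to arm gives 0.048 to 0.050 (20,000 runs).

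**Bound.** With pairs of two, ρ cannot exceed 1, so DE cannot exceed 2. The size is then at most 2 × [1 − Φ(1.96/√2)] = 0.166.

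**Professional year.** Suppose year explains 10% of the variance and splits evenly, 15 per year per arm (both assumed). With ρ as a share of total variance, DE for same-arm pairs becomes about 0.9 + ρ, that is 1.0, 1.2 and 1.4. The formula gives 0.050, 0.074 and 0.098; simulation gives 0.049, 0.074 and 0.100. So the balance by year can offset a small pair correlation but not a large one.

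**Which results could change.** SE = √((1.48² + 1.33²)/30) = 0.363. Same-arm pairs leave 15 pairs per arm, hence 28 df.

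- Planned difference: t = 1.68/0.363 = 4.62. At DE 1.5, t = 4.62/√1.5 = 3.78, p = 0.0008 on 28 df. At the bound of 2, t = 3.27, p = 0.003.
- Half that difference, 0.84 (illustrative): t = 2.31, p = 0.024 on the planned 58 df. At DE 1.5, t = 1.89, p = 0.069 on 28 df. The critical value on 28 df is 2.048, so p crosses 0.05 at DE = (2.312/2.048)² = 1.27, that is ρ of about 0.27.
- Cross-arm pairs (30 pairs, 29 df, critical value 2.045): at DE 0.5 a nominal t of 2.045 × √0.5 = 1.45 would already be significant. Its nominal p on 58 df is 0.15.

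**The case against.** The strongest reply is that the planned test may be right as it stands. The text says only that students were put in pairs, with no mention of arm. With 31 per arm at the start, pairing everyone within arm at the pre-test would leave one student over in each arm, so same-arm pairing cannot be presumed. Under arm-blind pairing the t-test is close to nominal, and the mixed model is slightly worse (simulated size about 5.4% to 5.8%). This stands as a possibility. It does not remove the point, because the plan does not say that pairing ignored arm.

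The scoring gap can also be argued down. Each student leads once and has a code, which suggests individual scores. That is a fair reading, but an individual score can still be correlated with the partner's.

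Three stronger readings are tempting, and the documents support none of them:

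- *The t-test produces too many false positives.* That needs same-arm pairs, which are not stated. Cross-arm pairs give the opposite error.
- *The error cannot be sized at all.* Only a point value is missing; pairs of two bound the size at about 17%.
- *Knowledge and self-efficacy are affected too, through the practice groups.* Neither is described as tested in pairs, and the 4-5 wording may be no more than a staffing ratio.

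**Conclusion.** The point holds for skill. The plan ignores two features of its own design, and the pairing rule that determines the direction of the error is not stated. Within the assumed range of ρ, the nominal 5% test could have a true size anywhere from 0.7% to 11%, or close to 5% if pairing ignored arm. Omitting year pulls the size down somewhat. All of this rests on assumed correlations and an assumed share of variance for year.

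A reader might infer that the main skill finding is unsafe. At the planned difference of 1.68 it is not: even at the bound of DE 2, p is about 0.003. The consequence is limited to borderline skill results, so this is a worthwhile correction rather than a fatal flaw.

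**What to change.** 1. **State** whether partners came from the same arm, how pairs were formed, and whose performance each checklist score describes.
2. **Skill:** use a linear mixed model with arm and professional year as fixed effects, a random intercept for evaluation pair, and Satterthwaite degrees of freedom. Simple alternatives for the pairing, without the year term, are a t-test on pair means if all pairs were same-arm, or a paired t-test if all were cross-arm.
3. **Knowledge and self-efficacy:** keep the planned comparison and add professional year.
4. **If pair identifiers were not kept,** say so. Report the skill t divided by √DE in both directions: DE 1.1 to 1.5 on 28 df (same-arm) and 0.5 to 0.9 on 29 df (cross-arm).
5. **Practice groups:** add a term only if membership was fixed. With groups of 5 and an assumed group ICC of 0.05 to 0.10, DE is about 1 ± ρ + 4 × ICC. That is 1 + 0.1 + 0.2 = 1.3 to 1 + 0.5 + 0.4 = 1.9 for same-arm pairs. For cross-arm pairs the limits are 1 − 0.5 + 0.2 = 0.7 and 1 − 0.1 + 0.4 = 1.3. With 6 or 7 groups per arm, use about 10 to 12 df.

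**Cost.** The change needs analysis wording and pair identifiers, which could have been logged against the student codes. The videos were deleted and follow-up is reported complete, so unlogged pairs may be lost and item 4 may be all that is possible. With same-arm pairs there is a small loss of precision, although simulated power at 1.68 with the pair term stays at about 95% or more. If pairing was arm-blind, size is slightly liberal, as noted above. A random intercept cannot represent negative within-pair correlation, nor correct an arm difference diluted by working with a partner from the other arm.
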